Official title: Stereotactic body radiation therapy with sequential S-1 for patients with locally advanced pancreatic cancer and poor medical conditions --a phase II clinical trial (SILAPANC trial)

NCT number: NCT02704143

Document state: 9th May 2020

1. Participants and eligibility

To be eligible for inclusion in the SILAPANC trial, all patients with clinical suspicion for pancreatic cancer, as presented in the imaging studies, were required to receive pathological examinations. If deemed necessary, further high-quality dedicated imaging of the pancreas should be performed before patients are enrolled into the study and undergo any study-related procedures. Biopsies were performed with fine needle aspiration *via* endoscopic ultrasound by experienced gastroenterologists. Specimen sections would be evaluated by two independent pathologists. After confirmed diagnosis of locally advanced pancreatic cancer by pathological examinations, patients should have the willingness and ability to provide an informed consent and comply with subsequent treatment plans, tests and other study procedures.

The following inclusion and exclusion criteria would be employed to preserve high internal validity and reduce risks of SBRT or S-1-induced adverse effects.

Inclusion criteria:

1. Unresectable without metastasis:

(a) Pancreatic head/uncinate process:

- (i) Solid tumor contact with the superior mesenteric artery $>180^\circ$;
- (ii) Solid tumor contact with the celiac axis $>180^\circ$;
- (iii) Solid tumor contact with the first jejunal superior mesenteric artery branch;
- (iv) Unreconstructible superior mesenteric vein/portal vein due to involvement or occlusion (can be due to tumor or bland thrombus);
- (v) Contact with most proximal draining jejunal branch into the superior mesenteric vein.

(b) Pancreatic body/tail:

- (i) Solid tumor contact of $>180^\circ$ with the superior mesenteric artery branch;
- (ii) Solid tumor contact with the celiac axis and aortic involvement;
- (iii) Unreconstructible superior mesenteric vein/portal vein to tumor involvement or occlusion (can be due to tumor or bland thrombus).

2. Without any other treatment before SBRT.

3. A life expectancy of >3 months.

4. ECOG: 2 or 3 points.

5. Age of more than 18 years old.

6. Blood routine examination: Absolute neutrophil count (ANC) $\geq 1.5 \times 10^9$ cells/L, leukocyte count $\geq 3.5 \times 10^9$ cells/L, platelets $\geq 70 \times 10^9$ cells/L, hemoglobin ≥ 8.0 g/dL.

7. Liver and kidney function tests: Albumin > 2.5 g/dL, total bilirubin < 3 mg/dL, creatinine < 2.0 mg/dL, AST $< 2.5 \times$ ULN (Upper Limit of Normal) (0-64 U/L), ALT $< 2.5 \times$ ULN (0-64 U/L).

8. INR < 2 (0.9-1.1).

9. Ability of the research subject or authorized legal representative to understand and the willingness to sign a written informed consent document.

Exclusion criteria:

1. Prior surgery, chemotherapy or radiation for the pancreatic cancer.
2. Evidences of metastatic disease such as nodal or distant metastases by abdomen CT and chest CT or FDG PET-CT.
3. Contraindication to receiving radiotherapy.
4. ECOG: 0-1 point.
5. Age<18
6. Abnormal results of blood routine examinations, liver and kidney function and coagulation tests.
7. Patients with active inflammatory bowel diseases or peptic ulcer.
8. Gastrointestinal bleeding or perforation within 6 months.
9. Heart failure: NYHA III-IV.
10. Women who are pregnant.
11. Participation in another clinical treatment trial while on study.
12. Patients in whom fiducial implantation was not possible.
13. Inability of the research subject or authorized legal representative to understand and the willingness to sign a written informed consent document.

Due to better diagnostic yield, safety and the potential lower risk of peritoneal seeding, endoscopic ultrasound-guided fine-needle aspiration is preferred for all patients

suspected of pancreatic cancer.

2. Doses of S-1

The doses of S-1 are calculated by the body surface. Hence, patients will receive S-1 orally, twice daily, at a dose of 80 mg/m^2 for 28 days, followed by a 14-day interval, which would repeat for 6 cycles. It was initiated one month after SBRT.

3. CT simulation for treatment planning

Each patient should fast for at least eight hours before the simulation. Vacuum bags are customized with patients in the supine position, according to the patient's body shape for immobilization during Cyberknife. SBRT is delivered *via* Cyberknife, an image-guided frameless stereotactic robotic radiosurgery system (Accuray Corporation, Sunnyvale CA), that consists of a linear accelerator mounted on a robot arm with six degrees of freedom. In this system, the confluence of a large number of non-isocentric pencil beams permits the treatment of irregularly shaped target volumes with rapid dose falloffs. Cyberknife tracking system automatically compensates for the alignment offset and patient motions by adjusting the treatment isocenter. In addition, a CT based treatment planning system is used at our institution. Then, plain CT and an enhanced pancreatic parenchymal CT are performed for radiation treatment planning and target delineations. CT images are acquired under breath hold (preferably end-expiratory). Pretreatment diagnostic imaging would be co-registered to the simulation CT in cases where the patient is unable to tolerate intravenous contrast. The scan range includes the

whole pancreas, at least 10 cm above and below the tumor. Spiral CT is performed with a slice thickness of 1.5 mm, and images are reconstructed in slices of 1.5 mm at most. Intravenous contrast enhancement is performed with an injection of 80-100 ml of iodixanol, a flow rate of 2.5 ml/sec, and a delay of 45-55 seconds; as acquired for the pancreatic parenchymal phase.

4. Registration and tracking

The co-registrations of biphasic CT images are based on fiducials and anatomical (spinal) fusion. Before CT simulation, fiducials should be implanted using endoscopic ultrasound or CT guidance. This is pivotal for treatment planning and delivery. CT simulation will be performed 7-10 days after fiducial placement. This time interval is required to avoid early fiducial marker displacement or migration. In order to improve the accuracy of the treatment planning, the recommended number of implanted fiducials is preferably close to 3-5. As a result, given that fiducials could simulate the spatial location and displacement of the tumor, which is attributable to respiration, motion tracking should be performed by means of the correlation with these seeds; and fiducial markers render the Synchrony system equipped in Cyberknife feasible. This allows for respiratory motion tracking during irradiation. Nevertheless, patients with high risk of bleeding, abdominal infection, pancreatitis or pancreatic fistula are contradictory to several fiducial implants. Hence, one fiducial plus X-sight spine and Synchrony Tracking technique would be alternatively used. Before treatment, direct digital radiography images of the spine would be applied to detect 6-D errors; and this

would be subsequently corrected for X-sight spine tracking on the patient's positioning.

This would enable fiducial tracking during treatment.

5. Treatment planning and target delineation

After CT simulation, CT images are transferred to the workstation where the target volumes are contoured by an attending radiation oncologist. Gross tumor volume (GTV) is delineated as a radiographically evident gross disease by contrast CT acquired from the portal-venous phase. At the discretion of the physician, clinical target volume (CTV) encompassing areas of the potential subclinical disease spread is also designated. In most cases, the CTV equals GTV. A 2-5 mm expansion margin is included to determine the planning target volume (PTV). When the tumor is adjacent to critical organs, the expansion of CTV should be avoided. Therefore, an individualized treatment plan would be developed based on tumor geometries and locations. Ninety percent of PTV should be covered by the prescription dose. The prescription isodose line is limited to 70-75%, which would restrict the tumor D_{max} . If dose level violates the constraint of SBRT, the patient would be considered as ineligible for this trial. The prescribed dose of PTV varies from 35-40Gy/5f with a single dose of 7-9Gy. In particular, these doses would be reduced if the tumor is approximately one-third or more of the duodenum or stomach circumference, or if the tumor abuts the bowel in only one area, as determined by the relationship of the tumor to the duodenum in axial, coronal and sagittal planes in CT scans, or the space between the tumor and the bowel wall is <3 mm. Normal tissue constraints are according to the American Association of Physicists in Medicine

guidelines in TG-101.

6. Follow-up

Patients are re-evaluated after Cyberknife every one month for the first three months, every 2-3 months for the next two years, and every six months for a total three years. Remissions of symptoms and radiation-related toxicities would be assessed. In addition, they would undergo laboratory tests, physical examinations, analysis of quality of life, and imaging studies every month within the first three months. Subsequent examinations in later follow-ups are the same.

7. Statistical analysis

All outcomes would be analyzed based on intention-to-treat principle. Continuous and categorical data were expressed as median (interquartile range, IQR) and n (%), respectively. Overall survival and progression free survival are calculated *via* the Kaplan-Meier method compared by the log-rank test. A two-sided α of less than 0.05 was considered statistically significant. Statistical testing is performed using SPSS version 20.0 (IBM Corp, Armonk, NY, USA).

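### Does the undefined bar on abnormal laboratory results contradict the AST, ALT and INR limits in the inclusion list?

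*Combined protocol and SAP*

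**What the plan says.** Section 1 (Participants and eligibility) gives an inclusion list and an exclusion list, which it says are "employed to preserve high internal validity and reduce risks of SBRT or S-1-induced adverse effects".

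The laboratory limits are in three inclusion items:

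- Inclusion 6, which opens "Blood routine examination: Absolute neutrophil count (ANC", sets minima for neutrophils, leukocytes, platelets and haemoglobin. No normal ranges are printed.
- Inclusion 7 sets limits for albumin, total bilirubin and creatinine, again without normal ranges. It then sets AST and ALT at less than 2.5 times the upper limit of normal. For AST the text after the multiple runs "ULN (Upper Limit of Normal) (0-64 U/L", and the same range follows ALT.
- Inclusion 8 requires INR below 2 and prints 0.9-1.1 in brackets.

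Exclusion 6 then lists "Abnormal results of blood routine examinations, liver and kidney function and coagulation tests". It has no threshold, no grade and no reference back to the inclusion list, and the term is defined nowhere else.

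**The concern.** A limit written as a multiple of the upper limit of normal admits values above normal by construction. An exclusion for abnormal values, taken at its word, removes those same values. A patient with moderately raised transaminases or INR would then satisfy inclusion 7 or 8 and be barred by exclusion 6, and nothing in the document says which item governs.

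If that were the true position, two screeners could reach opposite decisions on the same patient, and a reader of the results could not be sure how raised AST, ALT or INR was handled at entry. This would matter in a trial whose title names patients in poor medical condition, where out-of-range results can be expected. Section 7 also specifies analysis by intention to treat, so the rule used at entry fixes who is analysed.

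**Working it through.** The plan states no sample size, power or event count that bears on this point, so there is no figure to reproduce. The check compares the items and takes one step of arithmetic.

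**1. Where a clash can be shown.** Ten tests are named: neutrophils, leukocytes, platelets, haemoglobin, albumin, bilirubin, creatinine, AST, ALT and INR. A range is printed for three (AST, ALT, INR). For the other 10 - 3 = 7, a clash may exist but cannot be shown from the document.

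**2. Size of the overlap if the brackets are normal ranges (an assumption, since they are not labelled).**

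- AST and ALT: the upper limit of normal is 64 U/L, so the inclusion limit is 2.5 × 64 = 160 U/L. Values above 64 and below 160 U/L are admitted by inclusion 7 and abnormal under exclusion 6. The width is 160 - 64 = 96 U/L.
- INR: values above 1.1 and below 2 are admitted by inclusion 8 and abnormal under exclusion 6. The width is 2.0 - 1.1 = 0.9. Values below 0.9 are caught in the same way, because inclusion 8 has no lower bound.

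**3. Size if 0-64 U/L is instead the permitted range.** The upper limit of normal would be 64 / 2.5 = 25.6 U/L, and the overlap would run from above 25.6 up to 64 U/L. An overlap remains, but in a different place, so the 64-160 band depends on the assumption in step 2.

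**4. Why a percentage does not help.** The INR band is 0.9 / 2.0 = 45% of a span starting at 0, but 0.9 / (2.0 - 0.9) = 0.9 / 1.1 = 82% of a span starting at 0.9. The answer depends on the base chosen, and neither figure is a share of patients. The document gives no data from which to estimate that share.

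**5. Which reading the text supports.**

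| Subject | Inclusion item | Exclusion item |
|---|---|---|
| Earlier treatment | 2 | 1 |
| Metastasis | 1 | 2 |
| ECOG | 4 | 4 |
| Age | 5 | 5 |
| Consent | 9 | 13 |
| Blood count; liver and kidney; coagulation | 6; 7; 8 | 6 |

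Five exclusions besides item 6 turn an inclusion round. Exclusion 6 names its three subjects in the order in which inclusion 6, 7 and 8 present them. That is the pattern of a summary of the limits above it.

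**6. What the literal reading would do to the inclusion list.** If every value above normal were barred, the ceilings of 2.5 times the upper limit of normal and INR 2 could never decide a case, because exclusion 6 would already have removed anyone near them. Under the reading in step 3, the 64 U/L ceiling would be equally idle behind 25.6 U/L. A reading that empties three explicit numerical limits is the less likely one.

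**The case for a change.** The strongest reply is that the sensible reading is nowhere written down and that the two lists are not exact mirrors. Inclusion 5 reads "Age of more than 18 years old" while exclusion 5 bars only those under 18, so a patient aged exactly 18 is in neither list. Inclusion 4 reads "ECOG: 2 or 3 points" while exclusion 4 bars only 0-1, so ECOG 4 is in neither. If the mirroring fails there, it is fair to ask why it should be relied on for laboratory values.

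Those gaps differ in kind. A patient aged exactly 18, or with ECOG 4, fails an inclusion criterion and is ineligible, so nobody is both in and out. The gaps show an exclusion list drafted loosely. That fits exclusion 6 being a paraphrase at least as well as it fits a separate, stricter rule.

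A second reply has more force. Exclusion 6 speaks of whole panels, including coagulation tests in the plural, while inclusion 8 limits only INR. For a test that no inclusion item names, there is no limit to turn round, and the word abnormal stays undefined. This stands. Its reach is small: such results are left to the investigator's judgement at screening, and no definition, endpoint or analysis in the document refers to them.

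It also stands that a cross-reference from exclusion 6 to the inclusion limits would make the text cleaner. It would put on paper what a reader of the two lists would already infer.

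**Conclusion.** The inconsistency is real as a matter of wording, and it is a clerical slip. Exclusion 6 leaves its key word undefined and, read literally, clashes with inclusion 7 on AST and ALT and with inclusion 8 on INR, which is 3 of the 10 named tests. The bands are above 64 to below 160 U/L and above 1.1 to below 2, provided that the unlabelled brackets are normal ranges.

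No change to the plan follows. The matching subjects and order, the five other negated inclusions and the redundancy of the limits under the literal reading all point to exclusion 6 meaning failure of inclusion 6 to 8. The inclusion list prints numerical limits for each of these tests, so a reader can tell what was admitted, and another centre working from both lists would most naturally apply the same limits. Nothing in the document suggests that screening was in fact inconsistent. The survival analyses, the significance level and the analysis population rule in section 7 are the same under either reading.

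This conclusion rests on investigators having taken the natural reading, which the document supports but does not state. It takes no view on which laboratory limits are clinically right; that is for the sponsor.

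### Does ruling a patient ineligible at dose planning undermine the intention-to-treat analysis of survival?

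*Combined protocol and SAP*

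**What the plan says.** All references are to the combined protocol and SAP.

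- **Order of procedures.** Section 4, whose title refers to image registration and not patient registration, has fiducials implanted first. Then "CT simulation will be performed 7-10 days after fiducial placement". Section 5 places contouring and dose planning after that CT.
- **The rule at issue.** Section 5: "If dose level violates the constraint of SBRT, the patient would be considered as ineligible for this trial". It appears in neither the inclusion nor the exclusion list in Section 1.
- **A related exclusion.** Exclusion 12 in Section 1 reads "Patients in whom fiducial implantation was not possible".
- **Timing of enrolment.** The only text is in Section 1, where further pancreatic imaging, if judged necessary, is to be done "before patients are enrolled into the study and undergo any study-related procedures". No registration step or date is named.
- **Provisions that keep patients in.** Section 5: "In particular, these doses would be reduced if the tumor is approximately one-third or more of the duodenum or stomach circumference", with further bowel-proximity conditions. For patients at high risk from several implants, Section 4 says "one fiducial plus X-sight spine and Synchrony Tracking technique would be alternatively used".
- **Follow-up.** Section 6: "Patients are re-evaluated after Cyberknife every one month for the first three months", with later visits at longer intervals. It is silent on patients who never receive SBRT.
- **Analysis.** Section 7: "All outcomes would be analyzed based on intention-to-treat principle". OS and PFS are estimated by Kaplan-Meier. The intention-to-treat set and the time origin are not defined.

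**The concern.** A constraint violation cannot be known until at least 7-10 days after an invasive step. If a patient counts as enrolled before that step, calling the patient ineligible afterwards looks like removal after enrolment, which intention-to-treat is meant to prevent. Visits are scheduled only from Cyberknife, so such a patient has no stated visit or imaging schedule and could drop out of OS and PFS unnoticed.

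The documents describe no comparator arm that would share the same selection, so the absolute OS and PFS depend directly on who is counted. Planning failure depends on tumour geometry and location, so those who fail need not be a random subset. If they do worse, curves labelled intention-to-treat would flatter the treatment.

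**Working it through.** **Step 1: the order of events.** Sections 4 and 5 together give fiducials, then CT simulation 7-10 days later, then contouring and planning, then the eligibility rule. This part of the concern is correct.

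**Step 2: where enrolment falls.** There are two readings.

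| | Registration after plan acceptance | Enrolment before fiducials |
|---|---|---|
| Supporting text | Section 5 speaks of eligibility, not withdrawal or discontinuation. Exclusion 12 makes eligibility depend on implantation. | Word order in Section 1: enrolment is mentioned before study procedures. |
| Status of a planning failure | Screen failure | Enrolled patient |
| Intention-to-treat | Not breached | Breached only if the patient is left out of the analysis |
| Population described | Patients with an acceptable plan | All enrolled, if Section 7 is followed |

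The Section 1 sentence places optional diagnostic imaging before two events, enrolment and study procedures. It does not order those two against each other, so it only hints at the second reading. Neither reading is decisive. No sentence removes anyone from OS or PFS on either one.

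**Step 3: scale.** The documents give no sample size, survival assumption or planning-failure rate, so there is no figure of the plan to reproduce. Every input here is an assumption:

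- p, the share failing planning: 0.05 to 0.20
- survival in those kept: exponential with median 12 months, so L = ln 2/12 per month and 12-month OS is 50%
- HR, the hazard ratio of those dropped against those kept: 1.0 to 3.0

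Full-cohort survival is S(t) = (1 - p) exp(-L t) + p exp(-L HR t). At t = 12 this becomes (1 - p) × 0.5 + p × 0.5^HR. For p = 0.20 and HR = 3: 0.8 × 0.5 + 0.2 × 0.125 = 0.425.

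12-month OS in the full cohort (%), against 50.0 if failures are dropped:

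| p | HR 1.0 | HR 1.5 | HR 2.0 | HR 3.0 |
|---|---|---|---|---|
| 0.05 | 50.0 | 49.3 | 48.8 | 48.1 |
| 0.10 | 50.0 | 48.5 | 47.5 | 46.2 |
| 0.20 | 50.0 | 47.1 | 45.0 | 42.5 |

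Median in the full cohort (months), from S(t) = 0.5, against 12 if failures are dropped:

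| p | HR 1.0 | HR 1.5 | HR 2.0 | HR 3.0 |
|---|---|---|---|---|
| 0.05 | 12.00 | 11.75 | 11.57 | 11.36 |
| 0.10 | 12.00 | 11.50 | 11.16 | 10.72 |
| 0.20 | 12.00 | 11.03 | 10.37 | 9.52 |

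The largest overstatement of the median is 12/9.52 - 1 = 26%. It needs 20% failing and a threefold hazard together. At 5-10% failing and HR 1.5, 12-month OS shifts by 0.7-1.5 points.

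**Step 4: direction.** If those dropped had 12-month OS of 60%, the full-cohort value would be 0.5(1 - p) + 0.6p, that is 50.5%, 51.0% and 52.0% for p = 0.05, 0.10 and 0.20. The reported figure would then be 0.5-2.0 points too low.

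**Step 5: time origin.** If enrolment precedes fiducials and time is counted from SBRT, the interval omitted is at least 7/30.44 = 0.23 to 10/30.44 = 0.33 months. That is minor and also conditional.

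**The case for a change.** The best case for a change is that the two readings give different denominators and the documents do not choose between them. With no described comparator, the absolute curves are what a reader will use. The follow-up schedule starts at Cyberknife, which makes it easier to lose planning failures. Writing down the registration point, the analysis set and the time origin would cost a few sentences.

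Much of this is right. The silence is real, and a report that gives the number of planning and fiducial failures, with reasons, is easier to interpret than one that does not.

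Three things do not stand. First, a conflict with intention-to-treat needs both early enrolment and actual removal from the analysis, and the documents state neither. Second, a visit schedule that starts at SBRT does not show that survival goes unrecorded in patients who never reach it. Third, the most direct remedy, rewording the Section 5 sentence so that planning failures stay in the trial whatever treatment follows, would delete the only stated consequence of a constraint violation. That is a clinical-management rule, and a question about analysis sets is no reason to alter it.

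**Conclusion.** No change to the plan follows. The rule does act late, and the registration point, intention-to-treat set and time origin are unstated. That is missing detail, not a faulty analysis. If registration follows plan acceptance, planning failures are screen failures, and the curves describe patients with an acceptable plan. If it comes earlier, Section 7 already directs the analyst to keep every enrolled patient. An experienced analyst would apply whichever matches the registration log and would account for planning and fiducial failures in the patient flow.

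The size and direction of any effect cannot be determined from the documents. The range of 0-7.5 points in 12-month OS, and 0-26% in the median, rests wholly on assumed failure rates, exponential survival and hazard ratios of 1.0-3.0. It is zero at a hazard ratio of 1.0 and changes sign if those dropped do better. The dose-reduction provision and the one-fiducial option may also keep the number of failures down.

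This conclusion would not cover a trial in which patients were registered before planning and then left out of curves labelled intention-to-treat. Nothing in the documents says that was intended. Section 5 does not say how its dose-reduction and ineligibility statements fit together. The sponsor must reconcile them, but that is a separate clinical point with no bearing on the analysis set.

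### The SBRT fraction range (7-9 Gy) does not match the stated total at its upper end: 9 Gy × 5 is 45 Gy, not 40 Gy

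*Combined protocol and SAP*

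**What the plan says.** The dose is set in Section 5 (Treatment planning and target delineation): "The prescribed dose of PTV varies from 35-40Gy/5f with a single dose of 7-9Gy". That sentence gives the total, the number of fractions and the fraction size together. No other section gives a radiation dose.

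Section 5 also contains these limits on the plan:

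- **Isodose:** "The prescription isodose line is limited to 70-75" percent, in order to restrict the maximum dose in the tumor.
- **Eligibility:** a patient whose dose level breaks the SBRT constraints is treated as ineligible.
- **Proximity to bowel:** "these doses would be reduced if the tumor is approximately one-third or more of the duodenum or stomach circumference", and likewise where the tumor touches the bowel in one area or lies less than 3 mm from its wall. The size of the reduction is not given.
- **Normal tissue:** "Normal tissue constraints are according to the American Association of Physicists in Medicine" guidance in TG-101.

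The section does not say whether the five fractions are equal, and it describes no unequal or adaptive schedule.

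**The concern.** Total dose, number of fractions and dose per fraction are tied together by multiplication, so a sentence that gives all three can be checked against itself. The lower ends match exactly, which suggests that the fraction range was meant to be the total divided by five. The upper ends do not match.

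This sentence is the whole dose specification for one of the two study treatments, in patients enrolled because their performance status is poor (ECOG 2 or 3, Section 1). Someone working from the total reaches a maximum of 40 Gy. Someone working from the fraction size reaches 45 Gy. A monitor, or a center repeating the regimen, could not say with confidence whether a course using 9 Gy fractions complies with the protocol. Radiation-related toxicity is assessed at follow-up (Section 6), so the dose actually permitted also affects how those results are read.

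**Working it through.** **Inputs, all from Section 5.** Total 35-40 Gy and 5 fractions ("varies from 35-40Gy/5f"); dose per fraction 7-9 Gy ("with a single dose of 7-9Gy").

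**Step 1. Equal fractions.** Total = fractions × dose per fraction.

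- Lower end: 5 × 7 = 35 Gy. The plan's figure is reproduced.
- Upper end from the total: 40 / 5 = 8 Gy. The plan says 9 Gy.
- Upper end from the fraction size: 5 × 9 = 45 Gy. The plan says 40 Gy.
- Gap: (45 − 40) / 40 = 12.5%; equally, 9 / 8 = 1.125.

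Any equal fraction above 8 Gy, the upper half of the stated 7-9 Gy range, takes the total above 40 Gy.

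**Step 2. Unequal fractions.** With n fractions at 9 Gy and the rest at the 7 Gy minimum, total = 9n + 7(5 − n) = 35 + 2n.

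- n = 1: 37 Gy
- n = 2: 39 Gy
- n = 3: 41 Gy, above the limit

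At most two fractions can therefore be 9 Gy. One schedule that meets both ranges and reaches the maximum is 9 + 9 + 8 + 7 + 7 = 40 Gy.

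**Step 3. Do the other limits decide between 8 and 9 Gy?** If the isodose percentage is taken relative to the maximum dose, a 40 Gy prescription implies a maximum of 40 / 0.75 = 53.3 to 40 / 0.70 = 57.1 Gy, and 45 Gy implies 45 / 0.75 = 60.0 to 45 / 0.70 = 64.3 Gy. This limit scales with the prescription and does not cap it. TG-101 is cited for normal tissue constraints, not for a maximum prescription. The reduction near bowel starts from the disputed doses and only goes down, so it cannot explain a fraction above 8 Gy. The ineligibility rule states no prescription in Gy.

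**Step 4. Biological size of the gap.** Linear-quadratic biologically effective dose, BED = sum of d × (1 + d / (α/β)). The α/β values are assumptions; the document gives none.

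| Assumed α/β (Gy) | 5 × 9 Gy | 5 × 8 Gy | Difference |
|---|---|---|---|
| 2 | 247.5 | 200.0 | +23.8% |
| 3 | 180.0 | 146.7 | +22.7% |
| 5 | 126.0 | 104.0 | +21.2% |
| 8 | 95.6 | 80.0 | +19.5% |
| 10 | 85.5 | 72.0 | +18.8% |
| 12 | 78.75 | 66.7 | +18.1% |

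For 9 + 9 + 8 + 7 + 7 Gy the sum of squared fraction doses is 81 + 81 + 64 + 49 + 49 = 324. BED is then 40 + 324/10 = 72.4 Gy at α/β 10 (against 72.0) and 40 + 324/3 = 148.0 Gy at α/β 3 (against 146.7). An occasional 9 Gy fraction within a 40 Gy course changes little. What matters is the 45 Gy reading.

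**The case against.** The strongest reply is that this is not a strict contradiction. The sentence sets two limits, and both can be met: with equal fractions the usable range is simply 7-8 Gy and the 9 Gy bound is never reached; with unequal fractions, one or two at 9 Gy fit. The conflict needs equal fractions and needs the two upper ends to correspond, and the text states neither. A planner would also have to ignore the total in the same sentence to reach 45 Gy, a figure that appears nowhere. Individualized planning, the ineligibility rule and the normal tissue limits all stand in the way. The BED comparison assumes all five fractions at 9 Gy and applies the full prescription dose, so it says nothing direct about bowel or stomach toxicity. Finally, no eligibility threshold in Section 1 is given in Gy and the analysis in Section 7 uses no dose figure.

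Much of this stands, and it limits the severity. The total does exclude 45 Gy, the BED figures are a worst case and not a toxicity estimate, and no effect on an endpoint or analysis is shown. It does not remove the inconsistency. If fractions are equal, 9 Gy is an unreachable bound and so a wrong figure. If they are unequal, the protocol omits a schedule that it needs to state. The safeguards lower the risk but do not show which number was meant.

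**Conclusion.** The concern holds. On equal fractions, the stated ranges disagree at the upper end by 5 Gy in total or 1 Gy per fraction (12.5%). In BED terms the largest gap is about 18% to 20% for α/β of 8-12 Gy and 21% to 24% for α/β of 2-5 Gy, with those values assumed. The conclusion rests on equal fractions and on the two ranges being meant to correspond. The document does not confirm either, but the exact match at the lower end supports the second. Without the first assumption the ranges can be reconciled, but only with no more than two 9 Gy fractions and a schedule that is not described. Nothing here shows that any patient received 45 Gy. The point should be fixed because it is the only dose specification for the study radiotherapy and the document alone cannot settle it.

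**What to change.** The clinical team confirms what was intended, and Section 5 is corrected in one of three ways:

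- **The total governs:** keep 35-40 Gy in 5 fractions and change the single dose to 7-8 Gy.
- **9 Gy fractions are intended for the whole course:** change the total to 35-45 Gy.
- **Unequal fractions are intended:** say so, describe the schedule, and keep the 40 Gy limit.

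Delivered total and fraction doses are then checked against the corrected range. The cost is one changed figure (or, for the third option, a short description of the schedule) and a check of treatment records, with no extra patients or procedures.
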